3.6. Administration of Study Medication

On Day 1 (baseline visit), the study personnel will give to the patient the monthly box, containing 4 weekly boxes, each containing 7 daily boxes. Each daily box contains three marked vials (e.g., 1 - Morning, 2 - Afternoon and 3 - Evening) of frozen investigational medicinal product (IMP) solutions (-20 ± 5°C) containing:

This document is confidential.

- rhNGF at concentrations of 20 µg/mL, and/or
- vehicle (placebo).

Patient should bring the study medication, one monthly box, at home as soon as possible and immediately store it in a freezer at -20 ± 5 °C. The weekly box must be kept at 2-8°C for 7 days protected from light; the daily box can be kept at room temperature, before the patient will use the single vial for each instillation (both eyes) as long as 12 hours are not exceeded.

The administration route is ophthalmic; the first administration is to be applied by investigator at site.

In all patients, both eyes will be treated for a period of 4 weeks.

The dosing scheme of the different study groups is summarized below:

- Group 1: one drop of rhNGF 20 µg/mL will be instilled in both eyes three times daily (every 6-8 hours, e.g., 7:00 am, 02:00 pm; 09:00 pm).
- Group 2: one drop of rhNGF 20 µg/mL will be instilled in both eyes two times daily plus one drop (40 µL) of vehicle will be instilled in both eyes once daily (every 6-8 hours, e.g., 7:00 am, 02:00 pm; 09:00 pm).

NB: rhNGF will be instilled in the morning and in the evening while the vehicle will be instilled in the afternoon.

- Group 3: vehicle eye one drop will be instilled in both eyes three times daily (every 6-8 hours, e.g., 7:00 am, 02:00 pm; 09:00 pm).

3.7. Study Procedures and Flowchart

| Study procedures | Screening (Day-8) | Visit 1 Baseline Day 1* | Visit 2 Week 2 | Visit 3 End of treatment Week 4 ^a | Visit 4 follow- up Week 8 ^a | Visit 5 follow- up Week 12 ^b | Visit 6 follow- up Week 16 ^c |
|--|----------------------|-------------------------------|----------------------|---|--|---|---|
| Informed Consent | X | | | | | | |
| Inclusion/Exclusion Criteria | X | X | | | | | |
| Pregnancy Test | X | X | | | | | X |
| Randomization | | X | | | | | |
| Demographics | X | | | | | | |
| Ocular and Systemic Medical History | X | | | | | | |
| Previous Ocular And Systemic Medications | X | X | | | | | |
| SANDE | X | X | X | X | X | X | X |
| IDEEL | X | X | | X | X | X | X |
| EQ-5D-3L | X | X | | X | X | X | X |
| PGIC | | | | X | X | X | X |
| BCDVA | X | X | X | X | X | X | X |
| External Ocular Examination | X | X | X | X | X | X | X |
| Schirmer test I | X | X | X | X | X | X | X |
| Slit Lamp Examination | X | X | X | X | X | X | X |

This document is confidential.

| Study procedures | Screening (Day-8) | Visit 1 Baseline Day 1* | Visit 2 Week 2 | Visit 3 End of treatment Week 4 ^a | Visit 4 follow-up Week 8 ^a | Visit 5 follow-up Week 12 ^b | Visit 6 follow-up Week 16 ^c |
|---|----------------------|-------------------------------|-------------------|--|---|--|--|
| TFBUT | X | X | X | X | X | X | X |
| Fluorescein staining (NEI scale) | X | X | X | X | X | X | X |
| Schirmer test II | | X | | X | | | X |
| Confocal microscopy to assess goblet cells density ^d | | X | | X | | | X |
| Corneal endothelium and stroma evaluation as per confocal microscopy ^e | | X | | X | | | X |
| Study drug dispensation | | X ^f | | | | | |
| Verify patient study medication dosing compliance | | | | X | | | |
| Concomitant Ocular And Systemic Medications | | | X | X | X | X | X |
| Frequency of preservative-free artificial tears use (n° drops/day) | | | X ^g | X ^g | X ^h | X ^h | X ^h |
| Check and retrieval of patient's diary | | | X ⁱ | X | X | X | X |
| Record AEs | X | X | X | X | X | X | X |

*) visit window of +2 days **a**) Visit window of \pm 2 days; **b**) Visit window of \pm 4 days; **c**) Visit window of \pm 7 days; **d**) only selected sites; **e**) Only the sites having a confocal microscope will do this type of evaluation; **f**) a monthly box will be given to the patients; **g**) During the treatment period patients can use, if strictly needed, the preservative-free artificial tears; **h**) During the follow up period it is allowed to use the preservative-free artificial tears; **i**) During the Visit 2, Week 2, the PI or a delegate must only check if the patient has correctly completed the diary.

This document is confidential.

4. Endpoints

4.1. Primary Efficacy Endpoint

- Change from baseline in Schirmer test I (without anesthesia) versus Week 4.

4.2. Secondary Efficacy Endpoints

- Change from baseline in Symptoms questionnaire (SANDE) scores for severity and frequency assessed at 4 weeks of treatment;
- Change from baseline in Schirmer test II (with anesthesia) versus Week 4;
- Change from baseline in corneal and conjunctiva vital staining with fluorescein (NEI scales) versus Week 4;
- Change from baseline in TFBUT versus Week 4;
- Number of patients who experienced a worsening in symptom scores (SANDE) and/or NEI score $\geq 50\%$ as assessed at Week 4;
- Quality of life (Impact of Dry Eye on Everyday Life (IDEEL) questionnaire);
- Patient Global Impression of Change (PGIC);
- EQ-5D-3L.

4.3. Exploratory Endpoints

- Correlation between sign and symptoms scores;
- Proportion and frequency of preservative-free artificial tears use (n° drops/day) during the treatment period;
- Frequency of preservative-free artificial tears use (n° drops/day) during the follow up period.
- Change from baseline in Schirmer test I (without anesthesia) versus Week 2;
- Change from baseline in Symptoms questionnaire (SANDE) scores for severity and frequency assessed at 2 weeks of treatment;
- Change from baseline in Corneal and conjunctiva vital staining with fluorescein (NEI score) versus Week 2;
- Change from baseline in TFBUT versus Week 2;
- Number of patients who experienced a worsening in symptom scores (SANDE) and/or NEI score $\geq 50\%$ as assessed at Week 2;
- Change from baseline in goblet cells density versus Week 4.

4.4. Safety Endpoints

- Incidence and frequency of treatment-emergent adverse events (TEAEs), assessed throughout the study.

This document is confidential.

5. Analysis Sets

5.1. Enrolled Set

The Enrolled Set will consist of all patients who signed the ICF.
This analysis set will be used for patients disposition and some listings.

5.2. Randomized Set

The Randomized Set will consist of all patients who signed the ICF and were subsequently randomized into the study, regardless of study treatment administration.

5.3. Safety Analysis Set

The Safety Analysis Set (SAF) will consist of all patients in the Randomized Set who took at least one dose of investigational product (IP) . This analysis set will be used for the safety analysis. Patients will be analyzed according to the treatment received.

5.4. Full Analysis Set

Full Analysis Set (FAS) will consist of all patients randomized who took at least one dose of IP and who have at least one post-baseline efficacy measurement for the primary endpoint. This analysis set will be used for the primary efficacy analysis. Patients will be analyzed according to the randomized treatment.

5.5. Per Protocol Set

Per Protocol Set (PP) will consist of all patients in the FAS who fulfil the study protocol requirements in terms of IMP intake and collection of primary efficacy data and with no major deviations that may affect study results. This analysis set will be used for supportive efficacy analysis.

Patients will be evaluated according to the treatment dose they will actually receive.

5.6. Protocol Deviations

Important protocol deviations will be collected in the eCRF and CTMS. Each instance of a protocol deviation will be determined to be either significant or not. Protocol deviations linked to COVID-19 will be identified with "COVID-19 XXXXXX".

The major protocol deviations include, but are not limited to, the following (to be finalized before database lock):

- Non compliance with IP administration (less than 80% or more than 120%);
- missing primary efficacy data;
- Major deviation from inclusion/exclusion criteria (eligibility violations) (will be defined in blind conditions in the last blind data review meeting before database lock);
- intake of prohibited medications.

Protocol deviations will be reviewed during the course of the study and prior to database lock.

Patients with any major protocol deviations listed above will not be included in the PP set.

Number (%) of patients with at least one major protocol deviation leading to exclusion of subject from the Per-protocol will be included in a summary table, using the FAS Set.

All protocol deviations will be listed for all patients in the Randomized Set, including their assignment of minor, major, and the date the deviation occurred.

Protocol deviations linked to COVID-19 will be listed on a separate listing in the Randomized Set.

This document is confidential.

6. General Aspects for Statistical Analysis

6.1. General Methods

- SAS Version 9.4 or higher will be used for programming and production.
- Unless otherwise specified, summaries will be presented for each treatment and overall.
- Continuous variables will be summarized using the number of observations (n), n missing (when applicable), mean, standard deviation (SD), median, minimum, and maximum. Categorical variables will be summarized using number of observations (n), n missing (when applicable), frequency and percentages of patients. 95% and 99% confidence limits for the mean will be calculated based on the t-distribution, where indicated. The denominator will be based on the total number of patients in the treatment group or overall, or on the total number of subjects with non-missing data, as appropriate.
- All relevant patient data will be included in listings including assessments of unscheduled visits. All patients entered into the database will be included in patient data listings.
- See Sections 15 and 17 for the definition of planned summary tables and listings. Templates for each unique table and patient listing are provided in a separate document.

6.2. Key Definitions

6.2.1. Baseline Value

Unless otherwise specified, the baseline value for any variable will be the last value taken prior to the start of medication. This includes screening assessment. Unscheduled measurements prior to first administration date will be considered in the calculation of baseline values.

6.2.2. Change from Baseline and Percent Change from Baseline at a Post-Treatment Time Point

Change from baseline is defined as the difference between the post-treatment value and the baseline value.

Percent change from baseline is defined as $100^* (\text{change from baseline}) / \text{score at baseline}$.

6.2.3. Time Since Diagnosis of Dry Eye

Time since diagnosis of dry eye (in months) will be calculated as $12^* (\text{date of baseline} - \text{date of dry eye}) / 365.25$.

If the date of dry eye is partially missing (month and/or day), then the following rules will be used to impute the start date:

- Missing day: replace the missing day by 01.
- Missing month : replace missing month by January

6.2.4. Number of Days on Treatment

Number of days on treatment is calculated as $[(\text{date of last instillation of treatment} - \text{date of first instillation of treatment}) + 1]$.

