## 9.3. COMPLIANCE WITH IMP ADMINISTRATION

The assessment of patients' compliance to the IMP will be made by determining the number of study medication vials dispensed to the patient at Day 1 Visit 1 baseline and the number of unused study medication vials returned at Week 4 Visit 3 End of treatment. The percentage Compliance will be evaluated according to the following formula:

$$Overall \ compliance = 100 * \frac{(\text{Number of vials dispensed - Number of unused vials returned})}{3 * (\textit{Numbers of days on treatment})}$$

$$Compliance for the eligible \ eye = 100* \frac{(\text{Number of drops administered to the eligible eye})}{3*(\textit{Numbers of days on treatment})}$$

Gross non compliance will be defined as compliance lower than 80% or greater than 120% and in case of gross non compliance the patient will be excluded from the Per Protocol. Since this definition does not warrant that the study eye treatment is compliant, if indicated the SAP will contain further definitions based upon the diary card information.

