6.2.5. Compliance

Percentage Compliance (%) will be evaluated according to the following formula:

This document is confidential.

$$\text{Compliance for the eligible eye} = 100 * \frac{(\text{Number of drops administered to the eligible eye})}{3 * (\text{Numbers of days on treatment})}$$

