9.1. Extent of Exposure

The study drug administration (Day 1 to Week 4) will be captured in the patient diary including the administration of preservative-free artificial tears (Day 1 to Week 12).

The extent of exposure, otherwise referred to as the time from first instillation of study medication to last instillation of study medication is defined as:

Number of days on treatment = date of last instillation of treatment – date of first instillation of treatment +1

The data will be summarized by treatment group and presence/absence of primary Sjogren. A listing will be also provided.

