9.2. Treatment Compliance

The assessment of patients' compliance to the IMP will be made by determining the number of drops administered to the eligible eye (see section 6.2.5).

Gross noncompliance will be defined as compliance for the eligible eye lower than 80% or greater than 120% and in case of gross noncompliance the patient will be excluded from the Per Protocol set.

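### The compliance ratio divides by days actually dosed, so the 80–120% Per Protocol rule cannot register early stopping of treatment

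*SAP*

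**What the plan says.** SAP 6.2.4 gives the denominator: "Number of days on treatment is calculated as" the date of last instillation minus the date of first instillation, plus one. SAP 9.1 repeats it ("Number of days on treatment = date of last instillation of treatment – date of first instillation of treatment +1") and uses it as the extent of exposure.

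SAP 6.2.5 then says "Percentage Compliance (%) will be evaluated according to the following formula": 100 times the drops given to the eligible eye, divided by three times the days on treatment. SAP 9.2 sets the limit, "Gross noncompliance will be defined as compliance for the eligible eye lower than 80% or greater than 120" per cent, and removes such patients from the PP set. SAP 5.6 lists the same limits as a major deviation.

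Protocol 9.3 has the same limits ("Gross non compliance will be defined as compliance lower than 80% or greater than 120" per cent) and the same kind of denominator, but does not define days on treatment. It left room for the SAP to add diary-based definitions. The SAP added none, and SAP section 11 drops the vial-based measure because unused vials are not in the database. The eligible-eye ratio is therefore the only numeric test of intake left.

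On planned exposure, SAP 3.6 says "In all patients, both eyes will be treated for a period of 4 weeks" and "Each daily box contains three marked vials", one for each administration. SAP 5.5 requires PP patients to meet the protocol's requirements both for product intake and for primary data. Neither document sets a minimum treatment duration or a minimum share of planned drops.

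**The concern.** The PP set is meant to hold patients who took the product as the protocol requires. A ratio whose denominator ends on the last dosing day measures how regularly a patient dosed while still dosing. It does not measure how much of the four-week course was taken. Drops missed inside the dosing interval lower the score, but drops lost after the last one do not. Two patients with the same total exposure can thus receive opposite PP decisions.

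Early stoppers can reach Week 4. Protocol 6.3.1 asks for follow-up assessments after premature discontinuation unless consent is withdrawn, and Protocol 6.3.3 distinguishes stopping treatment from stopping observations. Such a patient can supply a Week 4 Schirmer I value after only part of the course.

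What is at stake is the reading of the PP results. If the drug works and the effect depends on exposure, keeping under-treated patients would tend to pull the PP estimate toward vehicle. Agreement between the Full Analysis Set (FAS) and PP results would then reassure more than it should. The PP analyses of Schirmer I and SANDE are marked as topline outputs (SAP section 15, Tables 14.2.1.2 and 14.2.2.1.2).

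**Working it through.** The plan states no compliance result to reproduce, so the check applies its formula to defined dosing patterns.

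**Inputs**
- Three instillations per day for 28 days (SAP 3.6): planned drops to the eligible eye = 3 × 28 = 84.
- SAP score = 100 × drops / (3 × (last − first + 1)) (SAP 6.2.4, 6.2.5).
- Share of plan = 100 × drops / 84.
- PP limits: 80% and 120% (SAP 5.6, 9.2).

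**Full dosing, then a stop on Day d**

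| Stop day | Drops | SAP score | Share of plan |
|---|---|---|---|
| 7 | 21 | 21/21 = 100% | 21/84 = 25.0% |
| 14 | 42 | 42/42 = 100% | 42/84 = 50.0% |
| 21 | 63 | 63/63 = 100% | 63/84 = 75.0% |
| 22 | 66 | 66/66 = 100% | 66/84 = 78.6% |
| 23 | 69 | 69/69 = 100% | 69/84 = 82.1% |

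Eighty per cent of plan is 0.8 × 84 = 67.2 drops. Against planned drops, a stop on or before Day 22 falls below the limit and a stop on Day 23 does not.

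**The same loss placed mid-course.** Fourteen dosed days around a 14-day gap, with first and last instillation 28 days apart inclusive: 42/(3 × 28) = 50%, so the patient is excluded. The same 42 drops taken on Days 1 to 14 score 100% and pass.

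**How far 100% is a ceiling.** The first drop is given at the site after the baseline examinations (Protocol 6.1), so the first day may hold fewer than three drops. Suppose three drops in all are lost on partial first and last days:
- Day 4: 9/12 = 75.0% (fails)
- Day 5: 12/15 = 80.0% (passes)
- Day 7: 18/21 = 85.7%
- Day 14: 39/42 = 92.9%

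Under that assumption a very short course can fail, but stops from Day 5 onward pass.

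**Sensitivity of the planned denominator to the Week 4 window.** If the visit falls on Day 26, planned drops to that visit are 3 × 26 = 78, and a Day 14 stop scores 42/78 = 53.8%. With the cap of 84 it scores 50.0%. Both are well under 80%. At the Day 26 edge the limit is 0.8 × 78 = 62.4 drops, so the last failing stop day moves from Day 22 to Day 20 (60/78 = 76.9%; Day 21 gives 63/78 = 80.8%).

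**The case against.** The strongest reply is that compliance is only one of several PP conditions.

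- SAP 5.5 has its own intake clause, the deviation list in SAP 5.6 is open until database lock, and Protocol 9.4.3 leaves PP exclusions to the Blind Data Review Meeting. A Day 7 stopper could be removed by any of these. This stands as a possibility, but no written rule does it, and a rule still to be written is not prespecification.
- Missing primary data is a listed exclusion. A patient who leaves before Week 4 has no Week 4 value, and SAP 6.3.1 specifies LOCF for the FAS only. This probably removes most patients who leave the study during treatment. It is not certain, because the SAP does not say whether missing means before or after LOCF. Protocol section 6 also schedules Week 4 and early exit as one visit, and SAP 6.4 applies no visit windows.
- A reader might infer that every early stopper scores 100% and stays in the PP set. The documents do not support that: 100% is a ceiling, and the missing-data rule covers many of these patients.
- A reader might also infer that early stopping would go unseen. Exposure is summarised by arm (Table 14.1.5.2), discontinuations are tabulated with reasons (SAP 7.1), and drug administration is listed (Listing 16.2.5.1). The blindness is in the PP rule, not in the reporting.
- The PP set is supportive, and the primary analysis on the FAS is untouched. This stands in full.

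**Conclusion.** The PP compliance rule is wrong as written. It cannot register truncation of treatment, and it treats equal losses differently according to where they fall. The gap is confined to patients who stop the drops early, have an observed Week 4 Schirmer I value, and are not flagged at blind review.

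For such a patient the score can reach 100% with as little as 25% of planned drops (Day 7 stop) and with up to 78.6% (Day 22 stop). These figures assume three drops on every dosed day. Taking 80% of 84 drops as the yardstick carries the plan's own limit over to planned exposure; neither document states it in that form.

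The number of patients affected cannot be computed. SAP section 2 reports 44 early terminations among 256 randomized by 9 March 2020 (44/256 = 17.2%). It would be tempting to read this as the size of the problem, but it covers the whole study, including 12 weeks off drug, and does not separate patients who stopped drops yet attended Week 4. Any dilution of the PP estimate is likewise conditional and unquantified.

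**What to change.** Before database lock:

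- In SAP 5.6, 6.2.5 and 9.2, base the 80–120% PP rule on planned drops. The denominator is 3 × 28, or 3 × the days from first instillation to a Week 4 visit inside the Day 28 ± 2 window if that is shorter. It must never run to an early-exit visit, since that would shorten the denominator again and restore the defect.
- In SAP 5.6, define missing primary data as no observed Week 4 Schirmer I value, before any LOCF.
- Keep the present ratio as a descriptive measure of compliance while on treatment.

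Protocol 9.3 leaves days on treatment undefined and lets the SAP add definitions, so the SAP can carry the change. Record it in SAP section 11.

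The cost is one formula and a sentence or two. The PP set may become slightly smaller, and it will select more explicitly on behaviour after randomization, which any PP set does. The FAS analysis does not change.

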6.2.5. Compliance

Percentage Compliance (%) will be evaluated according to the following formula:

This document is confidential.

$$\text{Compliance for the eligible eye} = 100 * \frac{(\text{Number of drops administered to the eligible eye})}{3 * (\text{Numbers of days on treatment})}$$

6.2.6. Number of Drops/Day

Drops/day during treatment period is defined as [sum of drops during treatment period / (date of Week 4 or date of last visit during treatment period – date of baseline +1)].

Drops/day during follow up period is defined as [sum of drops during follow up period / (date of Week 16 or date of last visit during follow up period – date of Week 4 + 1)].

6.3. Missing Data

6.3.1. Missing Data for Efficacy

For Schirmer test I, Schirmer test II, SANDE, fluorescein staining and TFBUT, the LOCF method will be used for imputing missing data in the FAS set at Week 4.

For missing data at Week 4, the data from the previous visit (Week 2 or early discontinuation visit if during treatment period) will be used to estimate the missing value. If a patient has missing data for all post baseline visits, baseline will be carried forward (this cannot happen for the primary end-point because of the FAS definition).

Several sensitivity analyses will be performed concerning the primary analysis in case of many missing values (decision to be made at the final blind Data Review Meeting, before data base lock).

The following strategies will be applied: (a) an analysis restricted to the complete cases (only subjects having a full data set for the primary outcome will be considered); (b) an analysis of repeated measures performed on all subjects having at least one post-baseline efficacy measurement and assuming that missing data are distributed as missing at random (see Appendix 1 for the SAS code); (c) an analysis considering the worst case method (the worst possible value of the scale is assigned to missing values).

For IDEEL and EQ-5D-3L questionnaires, missing data will be imputed according to the questionnaire manuals.

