#### 6.3. EARLY WITHDRAWAL FROM THERAPY OR ASSESSMENT

# 6.3.1. Primary Reason For Discontinuation From The Study

A premature discontinuation will occur when a patient who signed the ICF ceases participation in the study, regardless of circumstances, before the completion of the study protocol procedures. Patients can be prematurely discontinued from the study for one of the following reasons:

- Adverse event (AE): Any significant AE that, in the opinion of the Investigator or concerned patient, is not compatible with study continuation.
- ➤ **Disease progression or worsening,** that according to the opinion of the Investigator is not compatible with study continuation..
- > Death.
- ➤ Lost to follow-up (Every effort must be made to contact the patient; a registered letter must be sent).
- Non-compliance with study drug: an indication that a patient has not agreed with or followed the instructions related to the study medication.
- ➤ Physician decision: a position, opinion or judgment reached after consideration by a physician with reference to the patient.
- ➤ Severe Protocol violation: an event or decision that stands in contrast to the guidelines set out by the protocol.
- > Study terminated by the Sponsor: an indication that a clinical study was stopped by Sponsor.
- ➤ Withdrawal of consent: study discontinuation requested by a patient for whatever reason.
- **Other reasons**, such as administrative reasons or pregnancy.

Before removal, each case should first be discussed with Dompé farmaceutici s.p.a.

The reasons for premature discontinuation from the study will be reflected on the Study Termination Record of the eCRF. Unless the patient has withdrawn consent, the follow up visit assessments should be performed as detailed in § 6.

The investigator should advise patients that prematurely discontinue on any therapies or treatments for their condition and refer them for further treatment as appropriate

Version No. 2.0 – Final 08/AUG/2019

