# 9.4.2. Reasons for exclusion from the Full Analysis Set

Reasons for the exclusion from the Full Analysis Set are the following:

- > failure to take at least one dose of the IMP at the study eye
- > lack of any efficacy data post enrollment.

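### The Full Analysis Set counts a Schirmer I reading at any post-baseline visit, but the Week 4 LOCF rule draws only on treatment-period visits, so some FAS patients have no value for the primary analysis

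*SAP*

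**What the plan says.** The primary endpoint in SAP 4.1 is "Change from baseline in Schirmer test I (without anesthesia) versus Week 4". SAP 8.1 bases the primary analysis on the FAS, with missing data replaced by LOCF.

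SAP 5.4 defines the FAS as randomized patients who took at least one dose and "who have at least one post-baseline efficacy measurement for the primary endpoint". It sets no time limit, and Protocol 9.4.1 has the same definition.

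The flowchart in SAP 3.7 schedules Schirmer I at all seven visits: "Schirmer test I | X | X | X | X | X | X | X". Five of these are post-baseline (Weeks 2, 4, 8, 12 and 16), and the last three fall after treatment has ended.

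SAP 6.3.1 gives the Week 4 rule in two steps:

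1. If Week 4 is missing, "the data from the previous visit (Week 2 or early discontinuation visit if during treatment period) will be used to estimate the missing value".
2. "If a patient has missing data for all post baseline visits, baseline will be carried forward". The parenthesis that follows says "this cannot happen for the primary end-point because of the FAS definition".

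The rule covers Schirmer I, Schirmer II, SANDE, fluorescein staining and TFBUT.

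**The concern.** The two definitions use different sets of visits. FAS membership looks at all post-baseline visits; the LOCF donor must come from the treatment period. The baseline fallback uses the wider set, so a single late reading is enough to switch it off. The parenthesis shows that the authors relied on the FAS definition to guarantee a usable Schirmer I value, and it does not.

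At stake is an undefined exclusion from the primary analysis of patients who missed every treatment-period measurement, for reasons that may be related to outcome. The programmer would have to choose between omission, baseline and an off-treatment value without guidance. The rule also orders patients oddly. For the secondary LOCF endpoints, an FAS patient with no post-baseline value at all is given no change from baseline, while one who came back in follow-up is given nothing.

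**Working it through.** **Inputs.** FAS definition (SAP 5.4); donor visits and fallback trigger (SAP 6.3.1); visit schedule (SAP 3.7); primary model (SAP Appendix I); delta 5.3 mm, SD 10.78, one-sided alpha 0.025, 87 or 76 per group (SAP 3.4).

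**Step 1: Schirmer I patterns.** Each of the five post-baseline visits is either observed or missing, giving 2^5 = 32 patterns. Applying the rules literally, before considering any discontinuation visit:

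| Pattern | Count | Result |
|---|---|---|
| Week 4 observed | 2^4 = 16 | Week 4 used |
| Week 4 missing, Week 2 observed | 2^3 = 8 | Week 2 carried forward |
| All five missing | 1 | Not in the FAS |
| Weeks 2 and 4 missing, at least one of Weeks 8, 12, 16 observed | 2^3 − 1 = 7 | In the FAS; no donor; fallback not triggered |

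A discontinuation visit within the treatment period would rescue a patient in any of the last seven patterns. Without one, no Week 4 value is defined. A termination visit after the treatment period does not help: it satisfies the FAS definition but is not a permitted donor.

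**Step 2: does another rule close the gap?** SAP 8.1 names only LOCF. SAP 6.4 uses CRF visits without windows, so a late visit is not re-mapped to Week 4. The Appendix I macro fits PROC GLM to one change value per patient, and a patient with a missing response does not enter the fit. The omission is thus inferred from the rules and the code; the SAP does not state it.

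**Step 3: can such patients arise?** Protocol 6.3.1 says of discontinued patients: "Unless the patient has withdrawn consent, the follow up visit assessments should be performed". Protocol 6.3.2 requests a termination visit only as far as possible. SAP 2.1 lets a telephone contact replace a site visit during COVID-19 and lists questionnaires, diaries and a safety review, but no Schirmer test. SAP 2 reports 27 patients ongoing and 5 not yet randomized at that time. It does not say how many of these missed a treatment-period reading.

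**Step 4: Schirmer II.** It is scheduled post-baseline only at Weeks 4 and 16, so there are 2^2 = 4 patterns. In two, Week 4 is observed. In one, both are missing, and an FAS patient gets baseline carried forward. In the fourth, Week 4 is missing and Week 16 observed: there is no scheduled donor and no fallback. Every such patient lacks a value unless a treatment-period discontinuation visit supplies one.

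**Step 5: size, on power.** First, the plan's own figures by the two-sample normal formula. n = 2(1.960 + 1.282)^2 × (10.78/5.3)^2 = 86.9, rounded up to 87, as stated. Power = Φ(5.3/(10.78√(2/n)) − 1.960); at n = 76 this is Φ(3.031 − 1.960) = 85.8%, which agrees with the stated figure of at least 85%.

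The affected fraction is not in the documents, so a range is assumed, equal in each arm:

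| Fraction without a Week 4 value | Power from 76 per group | Power from 87 per group |
|---|---|---|
| 0% | 85.8% | 90.0% |
| 1% | 85.4% | 89.7% |
| 2% | 85.1% | 89.4% |
| 3% | 84.7% | 89.1% |
| 5% | 84.0% | 88.5% |
| 10% | 82.0% | 86.8% |

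These figures show the loss of patients only. They say nothing about bias.

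**The case against.** **The parenthesis is not false.** It refers to patients with every post-baseline value missing, and the FAS definition does rule them out for Schirmer I. This stands in full. The defect is an uncovered case, not a false statement.

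**Most early stoppers will have a donor.** Protocol 6.3.2 asks for a termination visit, its assessments in Protocol 6.2 include Schirmer I, and Protocol 3.3 pairs Week 4 with early withdrawal. Someone who stops the drops but stays in the study is still due at Weeks 2 and 4. The gap therefore needs an unusual pattern: all treatment-period readings missed, then a return. This stands as to frequency, but the visit is not assured, and Schirmer II needs only Week 4 to be missed.

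**The FAS may have been meant to require a reading by Week 4.** A measurement for the primary endpoint could be read that way, which would close the gap for Schirmer I. Neither document says so. Protocol 9.4.2 points the other way: besides failure to dose the study eye, its only reason for exclusion is "lack of any efficacy data post enrollment". This reading would also leave Schirmer II unresolved.

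**The omission would be visible.** SAP 6.1 provides for counts of missing values, SAP 13.2.4 separates N from n, and the Williams macro prints the number of observations per group. This stands: a reader might infer that patients vanish silently, and the outputs do not support that. Visibility does not supply the missing rule.

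**Sensitivity analyses could retain these patients.** The repeated-measures and worst-case analyses in SAP 6.3.1 might do so, but they are run only if many values are missing, and they are not primary.

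**Conclusion.** The misalignment is real and worth correcting before database lock, but it is narrow. It rests on a literal reading of SAP 5.4 and 6.3.1 and on the way PROC GLM treats a missing response. The number of patients affected is not given and is probably small; up to 5% per arm would cost under 2 points of power.

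A reader might go further and infer that the treatment effect is overstated by a calculable amount. The documents do not support that. They give no count of such patients by arm. The 44 early terminations among 256 randomized in SAP 2 are study-wide terminations, not patients with follow-up readings only. The 5.3 mm is a difference between treatments, so it cannot serve as one arm's mean change. The direction of any bias depends on how the omitted patients fared and on which arms they were in, and neither is known.

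**What to change.** In SAP 6.3.1, replace the fallback trigger with wording such as: *If a patient has no post-baseline value in the treatment period (Week 2, Week 4, or an early discontinuation visit in that period), baseline is carried forward; Week 8 to Week 16 values are not used.* Apply it to all five LOCF endpoints. Delete the parenthesis, which would no longer be true under the new trigger. Report by arm the number of patients imputed this way, so that the N of the primary ANOVA equals the FAS N.

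The cost is one sentence and a small change to the derivation code. The downside is that a few zero-change values enter the analysis, which may alter the estimated difference and the SD. The alternative, requiring a Schirmer I by Week 4 for FAS entry, also removes the ambiguity for the primary endpoint, but it excludes these patients and does not cure Schirmer II.
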